5 ELIGIBILITY CRITERIA

5.1 Inclusion criteria

- Patients of any age with DMD diagnosed more than 6 months ago;
- Patients included in the BNDMR (ORPHA code: 98896), who do not object to the collection of their data (see BNDMR 'Agreement to be contacted for a protocol') and who are alive at the time they are asked to participate in the study.

Identified patients are those present in the BNDMR with an up-to-date address at their follow-up center.

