7.3 Identification et quantification des ressources consommées

The resources consumed will be identified and quantified:

1. Non-reimbursable health resources

- Name and weekly quantity of OTC drugs consumed in a representative month;
- Name, type and quantity of other OTC products (e.g. small medical devices, oral nutritional supplements, etc.) purchased in a representative month;
- Number and type of paramedical consultations carried out in a representative month;
- Number and type of non-reimbursable technical equipment for disability compensation purchased since DMD diagnosis.

2. Ressources de la sphère médico-sociale

Medico-social costs include those incurred by the medico-social sector. This includes social and medico-social establishments and services (ESMS) and social action assistance.

There are two main types of establishment:

- Establishments and services for disabled adults;
- Establishments and services for disabled children and adolescents.

The following variables will be collected:

- Frequency, duration and type of stay in a social and medico-social institution in the last month;
- Number of visits to a medical-social service in the last month.

3. Support for schooling and Professional life

- Schooling programs;
- Socio-professional support services.

The following variables will be collected:

- Number and type of support staff (carers, special educators, social workers, etc.) in the last month;
- Type of schooling, specific assistance and how many hours, if not in which structure, and what additional costs in the last month;
- Working hours, support arrangements and how many hours over the past month.

4. Other non-medical resources

- Recours à une aide hors secteur sanitaire pour les actes de la vie quotidienne (ménagère, auxiliaire de vie, etc.), type et nombre d'heures hebdomadaires ;
- Aménagements réalisés au domicile, depuis le diagnostic ;
- Adaptation du(des) véhicule(s) et/ou acquisition d'un véhicule aménagé, depuis le diagnostic
- Modalité des transports non médicaux, fréquence et kilométrage hebdomadaire.

5. Informal help

- Number of caregivers over 18 years old in total, degree of kinship;
- Number of hours spent with the patient providing support for care, daily living activities, and instrumental activities of daily living.

6. Productivity loss

- For the primary caregiver: Changes in situation, absenteeism, and presenteeism related to DMD;

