- For the patient: Absenteeism and presenteeism (school or work) related to DMD.

7. Help and allocations

The allowances include disability compensation (PCH), compensatory allowance for a third party (ACTP), child disability education allowance (AEEH) and its supplements, adult disability allowance (AAH), and the increase for independent living (MVA).

The following variables will be collected:

- Allowances received, type, and total amount;
- Destination (compensation for non-medical costs, loss of productivity, etc.): not requested in the questionnaire; this item will be subject to a post hoc analysis

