7.4 Resource valorization

Direct medical and non-medical costs will be annualized, assuming consistent/representative resource use over the measurement period (months).

1. Non-reimbursable healthcare resources

- Weekly quantity valued at the average sale price;
- Quantity of other over-the-counter products (e.g., medical devices, oral nutritional supplements (ONS), etc.) valued at the average sale price;
- Number of hours of paramedical care valued at the corresponding wage/convention rate (if available);
- Quantity of technical equipment for disability compensation valued at the average sale price.

2. Medico-social resources

- Use of medico-social support: number of hours valued at the service rate, or, if unavailable, at the average hourly wage of equivalent professionals in France;
- Total costs of stays and consultations in medico-social facilities related to the specified medical condition within the medico-social sector.

3. Other non-medical resources

- Home adaptations: family expenses (lifetime);
- Modification of vehicles and/or purchase of an adapted vehicle: family expenses (lifetime);
- Non-medical transportation: weekly mileage valued according to the mileage reimbursement rate for personal vehicles.

4. Informal help

Care hours provided by caregivers valued at the cost of a replacement salary, according to the Proxy Good Method (PGM), and hours for activities of daily living valued at the average salary of a housekeeper.

5. Productivity loss

Lost work hours related to the DMD (Degenerative Motor Disorder) that do not pertain to caregiving, valued at the average hourly wage in France.

6. Assistance and allocations

Total monthly benefits related to DMD (Degenerative Motor Disorder) received by the patient and/or the family in the medico-social sphere.

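### Informal-help hours are not restricted to hours due to DMD, so ordinary help to young children can be costed as disease burden

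*Combined protocol and SAP*

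**What the plan says.** Section 7.3 item 5 collects, besides the number and kinship of adult caregivers, the "Number of hours spent with the patient providing support for care, daily living activities, and instrumental activities of daily living". Section 7.4 item 4 prices care hours at a replacement wage and "hours for activities of daily living valued at the average salary of a housekeeper". No hours are deducted. Table 2 (section 4.2.1) lists informal help for care and for daily activities, also without a limit.

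The next item is worded differently. Section 7.3 item 6 reads "For the primary caregiver: Changes in situation, absenteeism, and presenteeism related to DMD" and "For the patient: Absenteeism and presenteeism (school or work) related to DMD". In 7.4 item 5 the lost work hours are again tied to DMD, and only hours "that do not pertain to caregiving, valued at the average hourly wage in France" count. Benefits are tied to DMD in 7.4 item 6, though not in 7.3 item 7.

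Section 5.1 admits "Patients of any age with DMD diagnosed more than 6 months ago". Section 4.1 describes a non-comparative survey. Sections 8.3 and 8.4 contain no adjustment for the help that a healthy child of the same age receives. Section 2.2 sets the overall scope as costs tied to managing the disease.

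**The concern.** A young child needs help with washing, dressing and meals, and with every instrumental activity, whether or not he has DMD. If a parent reports those hours under item 5, they are multiplied by a wage and become part of the main criterion, the mean yearly cost per patient or family.

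The excess would not be spread evenly. It would sit mainly in the youngest, mostly ambulatory patients, so it would raise early-stage cost relative to later stages. That bears on the secondary objective of cost by severity and on the analysis by mobility level in 8.3. It also bears on the intended use: section 2.1 says that the results are to inform HAS and CEPS about a gene therapy whose ongoing trials recruit children aged 2 to under 4 and 4 to 7.

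Informal care carries real weight. Section 2.1 reports shares of total cost of 18% to 31%, 27%, and 42% to 50% in three of the cited studies that valued it. One cited US study compared mothers of patients with mothers of healthy children and found a wage loss of $41 a year while the child was ambulatory, against $23,995 beyond 4 years of mobility loss. That outcome is wages, not care hours, but it shows how small an estimate net of ordinary parenting can be at an early stage.

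**Working it through.** **1. The plan's own figure.** Section 8.1 gives a coefficient of variation of 1, relative precision of 15% and 171 pairs. With n = (z × CV / precision)² and z = 1.960, n = (1.960 × 1 / 0.15)² = 170.7, rounded up to 171. The confidence level is not stated; 95% two-sided reproduces the figure, whereas 90% would give 121. The sample size is not in dispute. That precision covers sampling error only, and a larger sample would not reduce a measurement bias.

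**2. The definitions side by side.**

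| Item | Limited to DMD when collected (7.3) | Limited to DMD when priced (7.4) |
|---|---|---|
| Informal help | No | No |
| Productivity loss | Yes | Yes |
| Benefits | No | Yes |

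With no comparison group and no age-norm adjustment, nothing later in the plan removes ordinary help once it has been reported.

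**3. Cost per young child (illustration).** The documents give no hourly rate and no hours of ordinary help, so both are assumed. Excess = hours per day × 365 × rate.
- 1 h at EUR 10: 1 × 365 × 10 = EUR 3,650 a year.
- 2 h at EUR 15: 2 × 365 × 15 = EUR 10,950 a year.

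**4. Effect on the overall mean (illustration).** Shift = share of young children × excess / true mean total. The share and the total are also assumed. With a total of EUR 40,000 and 2 h at EUR 15:
- share 10%: 1,095 / 40,000 = 2.7%
- share 25%: 2,737.5 / 40,000 = 6.8%
- share 40%: 4,380 / 40,000 = 11.0%

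Over a wider grid the shift runs from 0.10 × 3,650 / 60,000 = 0.6% to 0.40 × 29,200 / 20,000 = 58%, where EUR 29,200 is 4 h at EUR 20. So wide a range means that the size is undetermined.

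**5. Effect on the severity contrast (illustration).** Table 1 gives informal-care costs in the Portuguese study of EUR 9,996 (ambulatory) and EUR 20,772 (non-ambulatory), a ratio of 2.08. If 10%, 25% or 50% of the ambulatory figure were ordinary help, and none of the other, the ratio would be 20,772 / 8,996.4 = 2.31, 20,772 / 7,497 = 2.77, or 20,772 / 4,998 = 4.16. These shares are assumed; nothing in the documents says that the Portuguese figures contain ordinary help.

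**The case against.** The strongest reply is that silence is not a decision. The wording that respondents see is in the appended questionnaire, which was not available for this review. Section 6.3.2 says that its questions come from published instruments, and it may ask for DMD-related hours. Sections 2.2, 2.4 and 2.5 frame the whole study as disease-related cost. Other 7.3 items, such as over-the-counter products, home help and non-medical transport, also lack the qualifier, so its absence from item 5 says little about intent. This stands: a reader might infer that the plan chooses to cost all parenting hours, and the documents do not support that. They do leave the variable unrestricted, and general scope statements do not carry a restriction into its definition. Age-normal need also matters more for this item than for the others.

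A reader might also infer that informal care is the largest or second-largest component throughout the cited studies. It is not. In the Australian study it is 4,151 / 46,669 = 9%, with the main caregiver's help left out; one US study excluded it, the Spanish study did not value it, and the other US study lists it as not applicable.

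Nor should the per-child illustration be read as the bias in this study. The share of young children is unknown, and the exclusion in 5.2 of patients in interventional studies that modify care may lower it.

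Finally, month and year of birth are collected and a detailed SAP is still to be written (8.5), so an age-stratified analysis remains possible. But total hours alone cannot yield excess hours without outside norms.

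**Conclusion.** The point holds for the protocol text. Informal-help hours are not restricted to hours due to DMD, and no later step removes age-normal help. If the questionnaire follows the text, the bias is upward, concentrated in young ambulatory patients, and compresses the severity gradient. That direction rests only on young children needing ordinary help that their parents would report. The size cannot be derived from the documents: EUR 3,650 to 10,950 per young child per year, and the shifts in the overall mean, follow from assumed hours, wages, age mix and total cost. Whether ordinary parenting will in fact be counted depends on a questionnaire that could not be checked. The change should be made before the questionnaires are mailed.

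**What to change.** - In 7.3 item 5, define the variable as hours of help needed because of DMD, beyond what a person of the same age without DMD would need, recorded separately for care, daily activities and instrumental activities.
- In 7.4 item 4, apply the same rule, and name the price for instrumental activities, which that item does not mention separately.
- Check the appended questionnaire against this definition and reword its item before mailing if it differs. The pre-test in 6.3.2 can cover the item.
- Also record total hours and report them as a sensitivity analysis, which keeps the results comparable with published studies.

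The cost is small. If the questionnaire already asks for DMD-related hours beyond age-normal need, the definition and pricing rule need only be aligned in 7.3 and 7.4; if not, one item changes. Recording both quantities adds entries to the interview. The real downside is that respondents must judge the excess, which adds some reporting error. The research associate can help with this during the call that is already planned. The sample size stays at 171.

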4.2 Assessment criteria

4.2.1 Main criterion

Average annualized cost per patient/family.

Table 2 below shows the typology of all the costs considered in this study.

Table 2: typology of all study costs.

		Postes de coûts recueillis dans le cadre de l'étude 'CouDuMyo'
Coûts directs	Coûts médicaux non remboursables	
 ▪ Médicaments en vente libre ▪ Autres produits de santé en vente libre (ex : petits dispositifs médicaux, compléments nutritionnels oraux...) ▪ Equipements techniques de compensation du handicap ▪ Consultations de professionnels paramédicaux non pris en charge par l'Assurance Maladie (ex : ergothérapeute ou psychologue en ville...)
	Coûts liés à la sphère médico-sociale	
 ▪ Auxiliaire de vie, éducateurs spécialisés, assistants sociaux, accompagnement à la scolarité ▪ Hébergement en établissement médico-social ▪ Consultations dans des services médico-sociaux
	Coûts non-médicaux	
 ▪ Adaptation du domicile, adaptation du véhicule ▪ Transports non médicaux ▪ Aide informelle pour les soins (aidant familial, bénévole, autre) ▪ Aide informelle pour les activités quotidiennes ▪ Recours à une aide hors secteur sanitaire pour les actes de la vie quotidienne (ménagère, auxiliaire de vie, etc.)
Coûts indirects	Coûts indirects pour le patient	
 ▪ Pertes de productivité (adulte) ▪ Perte de jours d'école (enfant)
	Coûts indirects pour les aidants	
Pertes de temps dédié :
 
 ▪ à une activité professionnelle (aidant travaillant), ▪ ou de loisir (aidant non travaillant), 
hors temps consacré aux soins².

Aides financières	Coûts liés aux allocations/aides financières	Dispositifs permettant de financer (hors budget de l'Assurance Maladie dans le cadre de l'ALD) tout ou partie des coûts identifiés (ex : allocation compensatrice pour personne tierce (ACTP), allocation adultes handicapés (AAH), allocation d'éducation de l'enfant handicapé (AEEH), prestations de compensation du handicap (PCH)...)

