6.3.2 Questionnaire answering

The questions are taken from published questionnaires, and a validation of the questionnaire's comprehensibility and acceptability will be carried out on at least 2 child/caregiver and 2 adult/caregiver patients before the information letters are sent out [10].

The standardized questionnaire (see appendix) will be sent to patient/caregiver pairs with the information letter. This will enable participants to gather the information they need to answer the questionnaire.

A clinical research associate from the center which usually cares for the DMD patient or, failing that, from the URC Eco, will then contact the patient and/or his/her main carer by telephone. The interview, lasting a maximum of half an hour, will be based on the questionnaire and will ensure that the participant has understood the questions and that all the required data have been collected.

Variables intended to ensure representativeness or to enable sample adjustment will be collected at inclusion, including commune of residence (used only for adjustment), as well as:

- Patient characteristics: gender, month and year of birth, ambulatory or non-ambulatory status;
- Characteristics of the main caregiver: age, sex, relationship to the patient (degree of kinship, partner or other non-family relationship), family structure (couple, characteristics of other children, etc.).

Variables for cost analysis will also be collected (see chapter 7 + appended questionnaire).

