7 COST EVALUATION

7.1 Perspective

The societal perspective (integrating amounts financed beyond the perspective of compulsory health insurance, i.e. patient out-of-pocket expenses, non-reimbursed costs and lost productivity) will be retained.

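### For adult patients, 7.3 item 6 lists only absenteeism and presenteeism, so work never entered, stopped or reduced because of DMD is largely left out of the mean cost

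*Combined protocol and SAP*

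**What the plan says.** Productivity loss is item 6 of section 7.3 and has two adjacent lines. One reads "For the primary caregiver: Changes in situation, absenteeism, and presenteeism related to DMD". The other reads "For the patient: Absenteeism and presenteeism (school or work) related to DMD". No reason is given for the difference.

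The intended scope is wider. Table 2 (section 4.2.1) lists "Pertes de productivité (adulte" among the patient's indirect costs, meaning productivity losses of adults, and does not confine it to people with a job. The societal perspective in 7.1 takes in "patient out-of-pocket expenses, non-reimbursed costs and lost productivity". The valuation rule in 7.4 item 5 is "Lost work hours related to the DMD (Degenerative Motor Disorder) that do not pertain to caregiving, valued at the average hourly wage in France". It does not say from what baseline lost hours are counted.

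Two other sections collect related data. Item 3 of 7.3, under support for schooling and professional life, lists "Working hours, support arrangements and how many hours over the past month". Section 6.3.2 lists "Patient characteristics: gender, month and year of birth, ambulatory or non-ambulatory status". The same section adds "Variables for cost analysis will also be collected (see chapter 7 + appended questionnaire", so 7.3 is not the whole instrument. The questionnaire itself is not in the supplied text.

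**The concern.** In a work setting, absenteeism and presenteeism describe hours lost by someone who has a job. They are silent on the person who never took a job, left one, or works fewer hours. In DMD this matters because section 2.1 says walking is lost on average in early adolescence and that most children now reach adulthood, so part of the sample will be of working age with severe disability.

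The main criterion is the mean annualised cost per patient/family under a societal perspective. Leaving out this loss can only lower it, and recruiting more pairs would not help. The analysis by level of mobility (8.3) could also be affected if, as seems likely but is not documented, non-employment is more common among non-ambulatory adults. Reporting by cost type (4.2.2) would show the patient productivity line, but not what is absent from it.

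The protocol recognises the mechanism. In 2.1 it attributes the low indirect-cost share (6%) in a cited Australian study to a valuation that ignored reduced or stopped work. That remark concerned parents, so for patients it is an analogy only.

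**Working it through.** **Figures in the documents.** The plan gives no figure of its own for this loss. The nearest is the German study cited in 2.1 and Table 1:

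- 21,463 (adult patients) + 7,220 (caregivers) = 28,683 EUR indirect cost, as stated.
- 28,683 / 78,913 = 36.3% of total cost, matching the 36% stated.
- Adult-patient item: 21,463 / 28,683 = 74.8% of indirect cost and 21,463 / 78,913 = 27.2% of total cost.

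This shows that the item can be large. It does not show how much is due to non-employment: section 2.1 says the study worked from the respondent's salary and that the number of adults was not specified. The other patient figures in Table 1 (295, 495 and 956 EUR) come from a study that 2.1 describes as having too few respondents for a meaningful estimate.

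**What the listed variables capture.** Let *e* be usual working hours as a share of reference hours, and *a* the share of those hours lost to absenteeism and presenteeism. Assume the whole shortfall from reference hours is due to DMD.

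- Captured by item 6: *e·a*
- Full loss: (1 − *e*) + *e·a*
- Share captured: *e·a* / (1 − *e* + *e·a*)

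| *e* (assumed) | *a* = 0.05 | *a* = 0.20 |
|---|---|---|
| 0 | 0 / 1 = 0% | 0 / 1 = 0% |
| 0.5 | 0.025 / 0.525 = 4.8% | 0.10 / 0.60 = 16.7% |
| 0.75 | 0.0375 / 0.2875 = 13.0% | 0.15 / 0.40 = 37.5% |
| 1 | 100% | 100% |

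Capture is complete only for an adult already working full reference hours. The inputs are assumed, so the table shows the mechanism and not the size of the bias. A euro figure would need the adult share of the sample, their employment, the reference hours and the wage. The documents give none of these.

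**What can be rebuilt from variables already listed.** Item 3 gives hours worked and 6.3.2 gives age. With an external employment rate for that age, expected hours minus actual hours can be computed. Two things are still missing: whether a non-worker is entered as zero hours or left blank, and whether DMD is the reason. The BNDMR sampling variables in 9.1 do not include employment. The disability allowances in 7.3 item 7 are transfers, not lost output. Section 7.3 item 7 says their destination is not asked in the questionnaire and is left to a post hoc analysis.

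**The case against.** The strongest reply is that the instrument cannot be seen. Section 6.3.2 sends the reader to the appended questionnaire as well as to chapter 7, and says the questions come from published questionnaires, citing a French stroke study whose title concerns patients' productivity losses. A reader might infer that the answers will never be asked and the loss is irrecoverable. The documents do not support that. The questionnaire may ask more, and even without it the later SAP (8.5) could set reference hours and make a partial reconstruction from item 3 and date of birth. What the SAP could not add is attribution to DMD, if that was not asked.

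A reader might also infer that the protocol covers non-entry for caregivers and denies it to patients. That goes too far. Changes in situation is undefined; it reasonably covers stopping or reducing work, but not clearly never starting. Nor is the lack of reference hours specific to patients, since 7.4 item 5 gives none for caregivers either. Its wording is broad enough to include people out of work, but it does not say how to count their hours.

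The difference may have a rationale: caregivers usually have an earlier work situation to change from, whereas many patients do not. Whether to value non-entry at full reference hours is a choice of method to which the documents do not commit. This is a reason to report the line separately. It does not explain why stopping or reducing work is listed for one party and not the other.

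**Conclusion.** The concern holds as a gap between the scope in Table 2 and 7.1 and the variables listed in 7.3. If the list is followed as written, patient productivity loss is understated and so is the main criterion. The direction is clear if at least some adults are out of work, or work less, because of DMD. The size is unknown and no bound can be given.

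A reader might take the 74.8% from the German study as the amount at risk. It is not: it is the whole adult-patient item in another country, with an unknown part due to non-employment. Distortion by level of mobility is plausible inference, not something the documents show.

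The change should be made before interviews start. Confidence is medium because the questionnaire has not been seen; if it already asks about patients' employment and its cause, what remains is to align 7.3 with it and to state a counting rule. The sample size of 171 pairs is not affected.

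**What to change.** Before interviews start:

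1. In 7.3 item 6, extend changes in situation to adult patients: employment status, usual hours, and whether stopping, reducing or not entering work is due to DMD. Define the term so that non-entry is covered. If the questionnaire already asks this, align 7.3 with it.
2. In 7.3 item 3, record non-workers as zero hours, not as missing.
3. In 7.4 item 5 or the SAP, state the reference hours and working-age range used to count these hours, valued at the wage already specified. Keep absenteeism and presenteeism for those in work, counted against usual hours so that no hour enters twice.
4. If the cause is not asked, use a stated fallback: (general-population employment rate for age × reference hours) − actual hours. This estimates an average shortfall and does not attribute it to DMD person by person.
5. Because valuing non-entry depends on the method, report total cost, overall and by level of mobility, with and without this line.

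The cost is a few more questions within the interview limit (30 minutes in 6.3.2 but 60 in 6.1, which should be reconciled) and in the comprehensibility check that precedes the letters. It also brings reliance on an external reference figure and a larger, more variable indirect cost. Reporting both totals keeps that visible.
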